8.7.3 Quality of Life Assessments

The SF-12 v. 2 Health Survey is a shorter version of the SF-36 v. 2 Health Survey which uses just 12 questions to measure functional health and well-being from the patient's point of view. The SF-12 v. 2 covers the same eight health domains as the SF-36 v. 2 with one or two questions per domain (Ware, *et al.* 2009). The eight health domains covered by SF-12 v. 2 are: general health perceptions (GH), physical functioning (PF), role limitations due to physical health (RP), role limitations due to emotional problems (RE), bodily pain (BP), mental health (MH), vitality (VT), and social functioning (SF). Physical component summary (PCS) score and mental component summary (MCS) score are also calculated based on the individual answers.

The EQ-5D is a simple, brief and standardized instrument for use as a measure of health outcome (<http://www.euroqol.org/about-eq-5d.html>). The 5L version will be used in this study.

Subject are asked to fill in SF-12 v. 2 and EQ-5D quality of life surveys on paper on the following visits: Visit 1 (Week 0), Visit 4 (Week 4), Visit 8 (Week 12) and Visit 9, (Week 16).

For the calculation of SF-12 v. 2 health domain scores and summary scores, QualityMetric Health Outcomes™ Scoring Software 4.5.1 is used.

The baseline and post-baseline SF-12 v. 2 health domain and summary scores along with the change from baseline values will be described by summary statistics and presented by treatment group and visit. Individual health domain scores, summary scores and the scores of the individual questions in the survey will also be listed by visit and treatment group. Individual and mean health domain and summary scores will also be plotted by visit and treatment group.

Change from baseline in EQ-5D will be summarized by frequencies and percentages and tabulated by treatment group and question. The health assessments on visual analogue scale (VAS) with 0 being the worst imaginable health state and 100 being the best imaginable health state, will be described by summary statistics, the change from baseline values will also be summarized by treatment group and visit. The answers to all questions in the survey will be listed by visit. Mean EQ-5D assessments on VAS scale will also be plotted by visit and treatment group.

ITT population will be used for summarizing SF-12 v. 2 and EQ-5D results.

8.7.4 Biomarkers of disease activity

Several biomarkers of disease activity may be analysed in serum and in biopsy tissue at the time points specified in [Appendix 1](#), if available and deemed appropriate by the Sponsor. The biomarkers of interest include:

- Serum IL-15 (pg/mL);
- Serum Granzyme B (pg/mL);
- Serum CRP (mg/L);
- Serum albumin (g/dL);
- Flow NKG2D (% of positive cells; mean fluorescence intensity, MFI);
- Flow GzmB (% of positive cells; MFI);
- Flow CD122 (% of positive cells; MFI).

In addition, other exploratory biomarkers may be analysed, if deemed appropriate.

The biomarkers of disease activity will be described by summary statistics, along with the change from baseline values and tabulated by treatment group and visit, if applicable. All individual results will be listed by visit. Mean curves of biomarkers of disease activity will also be plotted by visit and treatment group, if applicable. Individual curves of relevant biomarkers may also be created, if deemed appropriate.

Flow cytometry biomarkers will be analysed internally by Celimmune.

ITT and PP analysis populations will be used for summarizing biomarker results depending on the type of marker (biopsy-derived, PP; continuous variable, ITT).

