10 CONCOMITANT MEDICATIONS

10.1 PROHIBITED MEDICATIONS

The following medications are not allowed at the time of randomization (Visit 1, Week 0/Day 0) or throughout the study:

- Systemic or intestinal immune suppressants, excluding steroids at a maximum dose of 20 mg of prednisone, prednisolone or equivalent per day and/or oral budesonide at a maximum dose of 9 mg/day. Systemic immune suppressants should not be used within the 3 months prior to randomization. Inhaled steroids for respiratory diseases such as asthma, and topical steroids are permitted.
- Chronic or continuous oral and IV antibiotics (>2 weeks use). Topical antibiotic use is allowed.

- Systemic antivirals
- Parenteral antifungals
- Anticoagulants in the week prior to the protocol-indicated biopsies (alternatively, local guidelines for the prevention of bleeding during endoscopy can be followed).
- Live vaccines.
- Investigational drugs or devices.

Note: After randomization, use of any of these medications is permitted if required for treatment of an AE. These medications may be started following discussion with and approval of the medical monitor. If discussion is not possible and approval has not been obtained prior to starting these medications, the situation should be discussed with the medical monitor promptly after treatment has been instituted to avoid classification as a protocol deviation. In the absence of discussion with the medical monitor, as described, starting these medications following randomization will be classified as a protocol deviation. If the prohibited concomitant medication is determined to interfere with the results of the study, withdrawal of the subject shall occur at the discretion of the Investigator or the sponsor.

Note: It is permitted to administer albumin if needed for the purpose of correcting excessive hypoalbuminemia in the context of protein-losing enteropathy, at the Investigator's discretion.

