14.5 BIOMARKERS OF DISEASE ACTIVITY

Several biomarkers of disease activity will be analyzed in serum (e.g., CRP, IL-15, sIL-15R), as exploratory indicators of disease activity and potential predictors of response to AMG 714.

Flow cytometry will be performed with fresh whole blood and with intestinal mucosal cells (IEL and *lamina propria* cells). Blood flow cytometry may be conducted on isolated peripheral blood mononuclear cells and/or directly in whole blood. Flow cytometry will be used to describe the phenotype of blood (including NK cells) and intestinal cells, including markers relevant to the enumeration (e.g., CD3, CD103) and function (e.g., NKG2D) of aberrant IELs.

Immunohistochemistry (IHC) will be performed in biopsy tissue to assess markers on IELs (e.g., NKG2D) and epithelial cells.

Biomarkers of IL-15 biology may also be analyzed in fresh biopsies, if available at sites with the relevant experimental capabilities.

In addition, other exploratory biomarkers may be analyzed at a later time in stored samples, including serum (for proteins, RNA), blood cell pellet (for future biomarkers using gene expression profiling and possibly lymphoma mutational analysis), biopsy fragments (for mRNA, protein, and possibly lymphoma mutational analysis), stool (gluten, microbiome), urine (gluten, metabolites). Future biomarker analysis will solely be for the purpose of celiac disease or AMG 714 research and will be reported separately and not in the clinical study report. The sample retention timelines will be described in the informed consent.

The DNA sample for HLA testing at screening, in subjects without pre-existing available HLA typing information, will be used solely for that purpose and will be destroyed after the result is obtained.

Blood samples for biomarkers must be obtained PRIOR to study drug administration at each time point listed in the schedule of events (Table 1). The time and date of sampling must be carefully recorded and reported in the eCRFs.

Select safety biomarkers will be evaluated as well as exploratory indicators of possible clinical efficacy, such as BMI (derived from the weight measures at every visit), serum albumin (patient with albumin being provided exogenously will be excluded from this analysis), hemoglobin, hematocrit.

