8.1 Data sets to be analysed

The populations for analysis will be the intention to treat (ITT, safety population, at least one dose of the investigational product received) and the per protocol population (PP, efficacy, i.e., available and evaluable pre- and post-biopsy information [Week 6]).

PP population: the PP population will exclude non-evaluable subjects and subjects with major protocol deviations thought to impact the ability to assess the effect of treatment. The PP population will also exclude atypical RCD-II patients (patients with a different phenotype of the aberrant IELs) for the purpose of analysis of Immunological Response 1 and 2; however, they will be included in all other efficacy assessment where a sensitivity analysis maybe performed excluding these subjects if these subjects are determined to be influential. Exclusion of subjects from the PP set will be reviewed, documented and approved before the study is unblinded to the study Sponsor.

Non-evaluable subjects will include subjects missing one of the two biopsies (or with biopsies of insufficient quality to generate valid data as determined by the Sponsor prior to database lock) and subjects dropping out of the study before Week 6. If a discontinuation occurs on or after Week 6 and the second biopsy is collected, then the subject is considered evaluable.

Atypical patients may also be analysed as a separate population if the results and sample size suggest such analysis is valuable.

The following major protocol deviations, as determined by the Sponsor prior to database lock, will lead to exclusion of subject from the PP population and will be thoroughly documented in the clinical study report:

- Intake of any forbidden concomitant medication or participation in other medical procedures, in case there is reason to believe, by the judgement of the Sponsor or investigator, that such concomitant medication/procedures would have a significant effect on the efficacy data obtained;
- Significant deviations from the inclusion/exclusion criteria of the study not previously approved by the Sponsor and determined prior to database lock to have impact on interpretation of results.

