ITT (safety) population: this population consists of all randomized subjects who have received at least one dose of the study drug. The safety population is by definition the same as the ITT population. If a subject had a misallocated treatment on a specific visit, observed upon unblinding, a secondary sensitivity analysis will be performed on as treated basis.

Main efficacy measures which require pre- and post-treatment biopsies will be analysed using the PP population (at least 2 biopsies, the second on Week 6 or later). Continuous efficacy variables will be analysed based on the ITT population. Demographic and baseline variables will be assessed using both ITT and PP populations. Safety parameters will be analysed using the ITT population. Compliance data will be reviewed to assure subjects were treated as randomized.

A detailed description of the study populations and subjects included will be given in the Subject Classification Document, which will be finalized before the database lock.

Table 1 Data sets to be used in the analysis

Primary variable ²	Secondary variables ^{1,2}	Exploratory/PD variables ¹	Safety variables	Demographic and baseline variables
PP	ITT PP	ITT PP	ITT	ITT PP

¹PP set used for biopsy-dependant variables and ITT for all other variables.

²PP population will exclude atypical RCD-II patients (patients with a different phenotype of the aberrant IELs) for the purpose of analysis of Immunological Response 1 and 2.

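### SAP 8.7.4 summarises serum albumin in all ITT subjects and omits the protocol 14.5 exclusion of patients given exogenous albumin

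*SAP*

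**What the plan says.** Protocol 14.5 introduces a group of measures with the words "Select safety biomarkers will be evaluated as well as exploratory indicators of possible clinical efficacy". Serum albumin is one of them, and it alone carries a population rule: "serum albumin (patient with albumin being provided exogenously will be excluded from this analysis").

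The rule answers a situation that the protocol foresees. A note in protocol 10.1 states: "It is permitted to administer albumin if needed for the purpose of correcting excessive hypoalbuminemia in the context of protein-losing enteropathy", at the investigator's discretion. Protocol 18.3 expects protein-losing enteropathy in this disease.

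SAP 8.7.4 lists "Serum albumin (g/dL") among the biomarkers of interest, without qualification. The planned output is stated for all of them: "The biomarkers of disease activity will be described by summary statistics, along with the change from baseline values and tabulated by treatment group and visit", where applicable. The analysis set follows from the type of marker: "ITT and PP analysis populations will be used for summarizing biomarker results depending on the type of marker (biopsy-derived, PP; continuous variable, ITT"). Serum albumin is continuous and not biopsy-derived, so it falls to ITT. SAP 8.1 defines that set: "this population consists of all randomized subjects who have received at least one dose of the study drug".

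**The concern.** Albumin replacement is given because albumin is low. A value measured after replacement reflects the infusion as well as the disease, so it is a poor marker of response. The protocol recognised this and removed such patients from the efficacy reading of albumin. An analyst working from the SAP alone would keep them in, and a subject who needed replacement could contribute a rise in albumin to the arm mean.

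What is at stake is one exploratory readout: whether the albumin table and mean curve by arm can be read as evidence on disease activity. Arms of 16 and 8 are small enough for one or two infused subjects to move a mean visibly. Each placebo subject carries 1/8 of the arm mean, twice the 1/16 carried by an AMG 714 subject.

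**Working it through.** The plan states no figure on this point, so there is none to reproduce. The check has two parts.

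**1. Does any other SAP text supply the exclusion?**

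- SAP 8.1, medication-based exclusion. It begins "Intake of any forbidden concomitant medication or participation in other medical procedures", and removes subjects from the PP set only. Albumin for hypoalbuminemia is permitted rather than forbidden, and its analysis set is ITT. The rule therefore does not reach it.
- SAP 8.8.6.2. Prior and concomitant medications are listed and are not linked to any biomarker analysis.
- SAP 8.9. The subgroup and sensitivity list names several prior and concomitant treatments, but not albumin use.
- SAP 12, changes made in V2.0. No entry says that the protocol 14.5 rule was considered and dropped.
- SAP Appendix 4 (table templates) and the Subject Classification Document named in SAP 8.1 are not in the available text. A footnote or rule there cannot be ruled out.

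Nothing available restores the exclusion, and nothing revokes it.

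**2. How far could it move the summary?**

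Inputs from the documents: 16 subjects on AMG 714 and 8 on placebo (SAP 3). Inputs that the documents do not give, and which are therefore assumptions:

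- x, the rise in measured albumin in an infused subject: 0.3 to 1.0 g/dL;
- a and p, the numbers infused on AMG 714 and on placebo.

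For infusion after baseline, with every subject contributing a value, the shift in the between-arm difference in mean change (AMG 714 minus placebo) is

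shift = x × (a/16 − p/8).

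| Infused on AMG 714 (a) | Infused on placebo (p) | Shift at x = 0.3 | Shift at x = 1.0 |
|---|---|---|---|
| 1 | 0 | 0.3 × 1/16 = +0.02 | 1.0 × 1/16 = +0.06 |
| 4 | 0 | 0.3 × 4/16 = +0.08 | 1.0 × 4/16 = +0.25 |
| 0 | 1 | −0.3 × 1/8 = −0.04 | −1.0 × 1/8 = −0.13 |
| 0 | 2 | −0.3 × 2/8 = −0.08 | −1.0 × 2/8 = −0.25 |
| 2 | 1 | 0.3 × (2/16 − 1/8) = 0 | 1.0 × (2/16 − 1/8) = 0 |

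All shifts are in g/dL. In the last row the difference is unaffected, but both arm means still rise by x/8, which is 0.04 to 0.13 g/dL.

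If the infusion comes before the baseline sample and its effect has gone by the later visit, baseline is too high by x. The subject's change is then too low by x, and every sign in the table reverses.

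**The case against.** The strongest reply is that this is an omission and not a contradiction. The SAP states that it is based on protocol version 3. Its ITT sentence is a general assignment for a list of markers. The protocol itself places a similar general rule (22.2, continuous variables on ITT) alongside the specific exclusion in 14.5. The two can be read together, with 14.5 still in force. That reading is possible, and it is why the documents do not support the inference that the SAP deliberately chose a different population. It does not make the SAP sufficient, however. Protocol 22 assigns the criteria for including subjects in an analysis to the SAP, and a programmer following 8.7.4 would find no exclusion there.

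The second reply concerns consequence, and most of it stands. SAP 8.7.4 makes the biomarker analyses optional, at the sponsor's judgement. It plans summaries, listings and curves, with no albumin responder definition, model or test. Individual biomarker results and concomitant medications are both listed, so a careful reader could trace the infused subjects. Albumin is also a safety laboratory test (SAP 8.8.2), and all ITT subjects belong in that table.

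Third, a reader might infer that infusions would fall mainly on failing placebo subjects, so that the SAP summary would hide a benefit of AMG 714. The documents do not support a direction. They do not say who would be infused, when, or in which arm. Larger shifts can be produced by assuming an infusion dose, a plasma volume and sampling soon after infusion, but none of these is in the documents.

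**Conclusion.** The point holds, at modest weight. The protocol excludes patients given exogenous albumin from the efficacy reading of serum albumin. The SAP, as far as its text is available, does not, and it records no decision to change. Followed literally, it would contaminate the albumin change-from-baseline summaries.

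The size is unknown. Under the assumed rise of 0.3 to 1.0 g/dL, the between-arm shift runs from zero (equal infused shares) to about 0.25 g/dL in either direction (2 of 8 on placebo only, or 4 of 16 on AMG 714 only). If no subject receives albumin, the issue is empty.

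It would be wrong to conclude that infused albumin will necessarily be reported as disease improvement, or that the trial's efficacy conclusion is at risk. The first depends on infusions occurring and on their timing. The second does not follow, because no primary or secondary endpoint uses serum albumin.

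**What to change.** In SAP 8.7.4, for the serum-albumin biomarker summary only:

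- apply the protocol 14.5 exclusion;
- identify exogenous albumin from the prior and concomitant medication records, including administration before the baseline sample;
- state whether the whole subject is removed or only values after administration, since protocol 14.5 can be read either way, and say what happens when the administration precedes baseline;
- tabulate the number of subjects given albumin, by arm;
- show the all-ITT albumin summary beside it as a sensitivity display. Administration during the study is a post-randomisation event, probably related to outcome, so the exclusion can itself bias the comparison.

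The all-ITT safety laboratory table under SAP 8.8.2 stays as it is.

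Carrying forward the last value before infusion should not be the main analysis. Protocol 22.3 rules out imputation beyond the missing data it describes. Carry-forward would also hold a subject at the low value that prompted the infusion, even if that subject later truly improved, and it is undefined for albumin given before baseline.

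The cost is a short SAP paragraph, one derivation from records already collected at every visit, and slightly fewer subjects in one exploratory summary. No protocol amendment is needed, because the rule is already in the protocol, and nothing in patient care changes.

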8.7.5 Pharmacokinetics (PK) and Exposure/Response (PK/PD)

Data for all subjects that receive at least one dose of AMG 714 and provide at least one quantifiable concentration value will be used in the PK analysis. Effects of major covariates (e.g., weight or BMI, BSA, sex, serum albumin and disease characteristics at baseline) on AMG 714 disposition will also be evaluated via modelling. Individual exposures at steady-state (AUC_{ss} and C_{trough,ss}) will be predicted from the developed population PK model and used for PK/PD assessments. These results will be provided in an independent PK Report.

In addition, AMG 714 concentrations in serum will be summarized. Summary statistics for concentrations will be calculated and the results tabulated by time point for AMG 714 treatment group. Levels of AMG 714 in serum will also be listed and mean results plotted by time point.

Finally, exposure/response (PK/PD) relationships will be investigated graphically.

For PK/PD assessments, individual patients' exposure measures obtained from the PK analysis will be graphically assessed with select PD endpoints and if associations are observed will be further elucidated with modelling and/or summaries by quartiles of exposure.

The following PD variables will be explored:

- Primary endpoint (Immunological Response 1: aberrant IELs by flow cytometry);
- Select secondary endpoints (Immunological Response 2: aberrant IELs by immunochemistry; Histological Response: VH:CD, total IEL count);
- Select PROs (CeD-PRO);
- Select biomarkers of disease activity (Serum IL-15).

Change from baseline to Week 12 for these variables will be plotted against individual predictions of steady-state exposure. For subjects with missing values at Week 12, earlier post-dose values will be used (if available), but those data points will be marked on the plots.

8.7.6 Celiac Disease Patient Reported Outcome (CeD PRO)

The CeD PRO questionnaire was developed to assess symptom severity in clinical trials in subjects with celiac disease. It is not validated in RCD-II. Items in the questionnaire were formulated based on one-on-one interviews with patients with celiac disease, thus they reflect the symptoms that patients consider part of their celiac disease experience. The questionnaire is designed as a self-administered daily diary, to be completed at the same time each day, and requires less than 10 minutes to complete. It includes nine items asking participants about the severity of celiac disease symptoms they may experience each day.

Participants are asked to rate their symptom severity on an 11-point, 0 to 10 scale; from “not experiencing the symptom” to “the worst possible symptom experience”. Symptoms include abdominal cramping, abdominal pain, bloating, gas, diarrhoea, loose stool, nausea, headache and tiredness.

Subjects will be asked to maintain a daily e-diary for the CeD PRO instrument from baseline to final study visit.

The total CeD PRO score is calculated as the sum of scores of all nine questions in CeD PRO questionnaire. The smaller the total CeD PRO score, the milder the symptoms of the subject. For modelling purposes, the total CeD PRO score on weekly level is also calculated (the weekly total score is calculated as the mean of total daily scores of a given subject).

The CeD PRO will be analysed using a linear mixed effects repeated measures model (MMRM) with the baseline value, treatment group, time point and a time point-by-treatment group interaction term as fixed effects with an underlying correlation structure between the time points that results in the best fit for the model. Subject will be included as a random effect.

Two separate models will be fitted: one for daily level data with time (days from baseline) as continuous variable and another for weekly level data with time (weeks from baseline) as a categorical variable.

For the daily level data, the following model will be fitted:

$$Y_{ijk} = \mu + \alpha_j + \beta \cdot \text{baseline CeD PRO}_{ij} + \gamma \cdot \text{day}_{ijk} + \lambda_{jk} + \eta_i + \varepsilon_{ijk},$$

where

Y_{ijk} is the total CeD PRO score for subject i ($i = 1, \dots, n_j$) from treatment group j ($j = 1, 2$) at day k ($k = 0, 1, \dots, 112$),

μ is the overall mean,

α_j is the fixed effect due to treatment j ,

β is the parameter estimate of the baseline total CeD PRO score,

γ is the parameter estimate of day,

λ_{jk} is the fixed interaction effect due to treatment j and day k ,

η_i is the random effect due to subject i ,

ε_{ijk} is the random error for subject i from treatment group j for day k .

Note that the proper functional form of the time (day) will be explored, e.g. square of day might be added.

The following SAS program will be used for carrying out the daily level analysis:

```
proc glimmix data=cedpro_d;
  class subjid trt;
  model cedpro_d = cedpro_d_bl trt day trt*day / solution;
  random _residual_ / subject=subjid type=AR(1);
```

```
estimate "AMG 714 vs Placebo" trt 1 -1 /alpha=0.05 cl;  
lsmeans trt /alpha=0.05 cl;  
ods output CovParms=Cov_Par LSMeans=LS_est Estimates=Eff_est  
FitStatistics=Fit_Stat ParameterEstimates=Par_est  
Tests3=Type_3;  
  
run;
```

For the weekly level data, the following model will be fitted:

$$Y_{ijk} = \mu + \alpha_j + \gamma_k + \lambda_{jk} + \beta \cdot \text{baseline CeD PRO}_{ij} + \eta_i + \varepsilon_{ijk},$$

where

Y_{ijk} is the total CeD PRO score for subject i ($i = 1, \dots, n_j$) from treatment group j ($j = 1, 2$) at week k ($k = 0, 1, \dots, 16$),

μ is the overall mean,

α_j is the fixed effect due to treatment j ,

γ_k is the fixed effect due to week k ,

λ_{jk} is the fixed interaction effect due to treatment j and week k ,

β is the parameter estimate of the baseline total CeD PRO score,

η_i is the random effect due to subject i ,

ε_{ijk} is the random error for subject i from treatment group j for week k .

The following SAS program will be used for carrying out the weekly level analysis:

```
proc glimmix data=cedpro_w;  
class subjid trt week (ref=FIRST);  
model cedpro_w = cedpro_w_bl trt week trt*week / solution;  
random _residual_ / subject=subjid type=AR(1);  
estimate "AMG 714 vs Placebo" trt 1 -1 /alpha=0.05 cl;  
estimate "Week 0: AMG 714 vs Placebo" trt 1 -1  
trt*week 0 0 0 0 0 0 0 0 0 0 0 0 0 0 0 0 0 1  
0 0 0 0 0 0 0 0 0 0 0 0 0 0 0 0 0 -1 /alpha=0.05 cl;  
estimate "Week 1: AMG 714 vs Placebo" trt 1 -1  
trt*week 1 0 0 0 0 0 0 0 0 0 0 0 0 0 0 0 0 0  
-1 0 0 0 0 0 0 0 0 0 0 0 0 0 0 0 0 0 /alpha=0.05 cl;  
...  
estimate "Week 16: AMG 714 vs Placebo" trt 1 -1  
trt*week 0 0 0 0 0 0 0 0 0 0 0 0 0 0 0 0 1 0  
0 0 0 0 0 0 0 0 0 0 0 0 0 0 0 0 -1 0 /alpha=0.05 cl;  
lsmeans trt /alpha=0.05 cl;  
lsmeans trt*week /alpha=0.05 cl;  
ods output CovParms=Cov_Par LSMeans=LS_est Estimates=Eff_est  
FitStatistics=Fit_Stat ParameterEstimates=Par_est  
Tests3=Type_3;  
  
run;
```

Due to the repeated structure of the data, the measurements within a subject will be correlated. Therefore, it is assumed that the overall covariance matrix of the response is block-diagonal (e.g. the observations between different subjects are not related, but the same correlation structure exists within subjects). In order to determine the covariance structure that best fits the data, the same model with different covariance structures is fitted. Initially, the models will be fitted assuming first-order autoregressive (AR(1)) variance-

covariance structure. Common within and between treatment variance components (compound symmetry (CS), and Toeplitz covariance structures) will be further explored to increase sensitivity of statistical tests. The best model will be chosen by comparing the Akaike Information Criterion (AIC) of the models with different covariance structures.

Note that the value of `type` will be changed according to which covariance structure is being fitted.

The modelling results (parameter estimates, covariance parameter estimates, estimated treatment effect, marginal means estimates and results of the check of assumptions) will be tabulated and 95% confidence intervals added, where appropriate. If the parametric assumptions are not met, then in addition to the above-specified model, a generalized estimating equation (GEE) approach will be used as well.

The baseline and post-baseline weekly total CeD PRO scores along with the change from baseline values will also be described by summary statistics and tabulated by treatment group. Change from baseline for the weekly CeD PRO scores of individual questions (calculated as the average score of a question within a week) will also be tabulated by week and treatment group and described by summary statistics. The scores of individual questions and the total daily CeD PRO scores will be listed, as well as the total and by question weekly CeD PRO scores. Mean curves of both the total weekly and daily CeD PRO scores as well as the individual questions will also be plotted by time point and treatment group.

A tabulation of the proportion of subjects with at least a 50% change from baseline for ≥ 6 weeks will be provided. This analysis will be done internally by Celimmune.

ITT population will be used for summarizing CeD PRO results.

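### Minor: the daily CeD PRO row labelled AMG 714 vs Placebo is a Day 0 difference, and SAP 8.2.1 lets a post-dose diary score replace a missing baseline, including for the secondary GSRS and CeD-GSRS

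*SAP*

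**What the plan says.** SAP 8.7.6 plans two CeD PRO models, "one for daily level data with time (days from baseline) as continuous variable" and a weekly one with week as a category. The daily program has the fixed effects "model cedpro_d = cedpro_d_bl trt day trt*day / solution", the single arm contrast "estimate 'AMG 714 vs Placebo' trt 1 -1 /alpha=0.05 cl" and the marginal means "lsmeans trt /alpha=0.05 cl". The equation runs the response over Days 0 to 112, so the Day 0 score is both an outcome row and the baseline covariate.

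On correlation the text states "Subject will be included as a random effect", while both CeD PRO programs code "random _residual_ / subject=subjid type=AR(1". The SAP starts from AR(1), also tries compound symmetry and Toeplitz, and chooses by AIC. The estimated treatment effect and the marginal means are tabulated together.

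SAP 8.2.1 defines change as the post-baseline value minus the pre-dose value. If the Week 0 or Day 0 score is missing, the earliest available score in the two weeks after treatment starts becomes the baseline. Failing that, the subject is non-evaluable for that test. Protocol 11.2.2 issues the e-diary at Visit 1, the first dosing visit, where the first GSRS and CeD PRO are completed. SAP 8.6.2 models GSRS and CeD-GSRS, both secondary, as change from baseline with baseline as a covariate.

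**The concern.** A row labelled AMG 714 vs Placebo in a table of treatment effects will be read as the drug effect. Here it describes a day on which the drug has had no time to act, and it will not agree with the marginal means printed next to it. It can hide an effect that builds up and exaggerate one that fades.

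The baseline rule has a different fault. No diary score exists before Visit 1, so any score entered later as a substitute comes after the first dose. An affected subject's change is then measured from a point already on treatment. A subject whose baseline is taken at Week 1 has a Week 1 change of exactly zero by construction.

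**Working it through.** The documents give no figure for either issue, so there is none to reproduce. Effect curves, variance shares and correlations below are my assumptions. SAS was not run; the reading of the contrast follows from the linear-model algebra and standard ESTIMATE rules.

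**A. What the contrast estimates.** With day continuous, the arm difference on day d is

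Δ(d) = (α_AMG − α_placebo) + d × (slope_AMG − slope_placebo).

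The coded row gives no coefficients for `trt*day`, so d = 0. LS means use the average day by default: (0 + 112)/2 = 56 with complete diaries. In the weekly program week is a class variable, so the same syntax averages over Weeks 0 to 16. One label thus names two quantities.

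For size, I took effect curves that are zero on Day 0, fitted a least-squares line a + b·d over Days 0 to 112, and divided by the true Day 84 effect. The Day 84 reading is a + 84b = a + 1.5 × [(a + 56b) − a], computed from unrounded values.

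| Assumed effect | Coded row (a) | LS-mean difference (a + 56b) | Line read at Day 84 |
|---|---|---|---|
| Linear throughout | 0% | 67% | 100% |
| Linear to Day 84, then flat | 6% | 62% | 90% |
| Approach with 4-week half-time | 28% | 75% | 99% |
| Approach with 2-week half-time | 47% | 83% | 101% |
| Peak at Week 2, then halving every 8 weeks | 187% | 135% | 109% |

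The true Day 0 effect is zero in every row. Any other value in the first column is misfit of the line.

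**B. Why the covariance matters once the contrast moves.** I simulated null trials of 16 vs 8 subjects over 113 days, with a subject share of 30–50% of variance and serial correlation 0.3–0.7 (210 trials per setting, Monte Carlo SE at most 3.4 points, nominal 5%).

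| Contrast | AR(1) kept | After the SAP's three-way AIC choice | Random intercept + AR(1) |
|---|---|---|---|
| Day 0, as coded | 7–24% | 4–8% | 2–4% |
| Day 84 (not in the plan) | 17–46% | about 26% at correlation 0.7 (23 of 90) | 4–6% |

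The weekly overall contrast rejects in 14–26% if AR(1) is kept and 5–8% after the AIC choice.

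A separate run with a larger subject share (SD 12 between and 6 within, so 144/180 = 80%) tested Day 56. AR(1) alone rejected in 53%, 47% and 31% at correlation 0.3, 0.6 and 0.8; compound symmetry rejected in 3.8–5.0%. Toeplitz was not fitted in that run, so the three-way figures rest on the first set only.

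**C. The substituted baseline.** The share of one subject's Week 12 change that is lost is the effect present at the substitute divided by the effect at Day 84.

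| Substitute | Linear onset | Two-week half-time |
|---|---|---|
| Week 1 | 1/12 = 8.3% | (1 − 2^−0.5)/(1 − 2^−6) = 29.8% |
| Week 2 | 2/12 = 16.7% | (1 − 2^−1)/(1 − 2^−6) = 50.8% |
| Day 1 (CeD PRO) | 1/84 = 1.2% | (1 − 2^(−1/14))/(1 − 2^−6) = 4.9% |

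Divided by 16 for the AMG 714 arm mean, a GSRS substitute costs 8.3/16 = 0.5% to 50.8/16 = 3.2% per affected subject, and a Day 1 CeD PRO substitute 0.1–0.3%. These are upper bounds, because adjusting for baseline gives back part of the loss when the baseline coefficient is below 1.

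GSRS asks about the past week (Protocol Appendix D). A full Week 1 form therefore covers only time after the first dose; a late entry on Days 1–6 still recalls some pre-dose days and loses less.

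**The case against.** CeD PRO is exploratory, and the SAP says of it "It is not validated in RCD-II". SAP 8.6.1 lets code change without an amendment, and SAP 8.7.6 adds "Note that the proper functional form of the time (day) will be explored, e.g. square of day might be added" and a GEE analysis if assumptions fail. The treatment-by-day slope, the weekly contrasts and the mean curves are also reported, so no reader depends on one row. All of this stands and keeps the point minor. None of it corrects the row: adding day squared still leaves `trt 1 -1` at Day 0.

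A reader might infer that the missing subject term means the planned list of structures excludes the stated model. The documents do not support that. The equation does not fix an AR(1) error. A random intercept with independent errors is marginally compound symmetry, and a random intercept plus AR(1) is a special case of Toeplitz; both structures are candidates. Under the planned choice the coded contrasts run near nominal (4–8%). The larger rates assume that AR(1) is kept, or test a day that the plan does not test.

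On the baseline, a reader might infer that 8.2.1 contradicts its own pre-dose formula or the protocol's limit on imputation (Protocol 22.3). That is too strong. The section gives a formula and then states which observed score serves as baseline, with the screening biopsy as another declared exception. The rule is disclosed in advance, and it applies only if a score is missed at a staffed visit. What remains is that the substitute is post-dose.

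**Conclusion.** Wrong as written, and minor. The Day 0 reading follows from the code and needs no assumption; its size (0–187% of the Day 84 effect) depends on the assumed curves. The baseline fallback is the part that reaches secondary endpoints. It takes about 8–30% (Week 1) or 17–51% (Week 2) off one subject's Week 12 change under the assumed onsets, which is at most 0.5–3.2% of the AMG 714 arm mean per affected subject.

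A reader might infer a material bias in GSRS. Losses as high as 25% would need 6 of 24 baselines substituted and the full effect present by Week 2, and no passage supports either. The primary endpoint and the Go/No-Go rule in Protocol 13.1, which rests on the two Immunological Responses, are unaffected.

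**What to change.** 1. Drop Day 0 from the daily response and name one post-dose day. For Day 84, code `trt 1 -1 trt*day 84 -84` and `lsmeans trt / at day=84 diff cl`. If a day-squared-by-treatment term is added, include its coefficients (84² = 7056, so `7056 -7056`).
2. In the same change, add a random intercept plus AR(1) (`random intercept / subject=subjid` beside the AR(1) residual) to the AIC candidates, keeping compound symmetry and Toeplitz. It is the parsimonious form of the stated subject effect; daily Toeplitz needs 113 parameters. Do not move the contrast without this step.
3. If Week 0 rows are dropped from the weekly model, rewrite every position-based week vector. With `ref=FIRST`, Week 0 now holds the last position; without it Week 1 would, and the coded Week 1 row would estimate Week 2.
4. Delete the post-dose fallback for diary scores wherever 8.2.1 states it. Then either apply the section's existing non-evaluable rule, or keep the subject through a constrained longitudinal model of raw scores (baseline as a response, equal arm means at baseline, no baseline covariate). Report how many subjects are affected.

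Cost: a few code lines, which SAP 8.6.1 allows without an amendment, and an amendment for the wording in 8.2.1. No new data and no patient burden. The non-evaluable option loses 1 of 16 AMG 714 subjects (6.25%) or 1 of 8 placebo subjects (12.5%) per missing score; the longitudinal model loses none.
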